We will implement all Bayesian models via Markov chain Monte Carlo methods (MCMC) by using R or SAS software. For SAS, the procedure will be PROC MCMC. For R, possible software is 'RJAGS' which is an interface to JAGS MCMC software, 'rstan,' 'rstanarm' and 'brms,' which are packages that interface with the Stan language. For each analysis, we will run three MCMC chains with randomly drawn starting values. We will use a burn-in of 3,000 iterations, with sampling from a further 30,000 iterations for each chain. Thinning will be used as necessary to reduce autocorrelation among the samples to improve posterior sampling. To monitor convergence, we will use trace plots and the Gelman-Rubin convergence diagnostic ($R_{hat} < 1.1$ indicating convergence) for all parameters.

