6.5 Bayesian Statistical Methods

6.5.1 Statistical Methods

Due to sample size limitation, the primary outcome (H1) and sensitivity analyses (1) and (2) will be analyzed using Bayesian methods in addition to the frequentist analyses to estimate the posterior distribution for all model parameters. Bayesian models will be fit using Markov chain Monte Carlo methods (MCMC) by using software such as PROC MCMC (SAS) or stan (RSTAN/RSTANARM package in R). Model parameter estimates will be generated by fitting three MCMC chains with randomly drawn starting chain. Each chain will involve 1,000 burn-in iterations and 1,000 additional iterations for each chain. Thinning will be used as necessary to reduce autocorrelation among the samples to produce good sampling of the posterior. Trace plots and Gelman-Rubin convergence diagnostics (Rhat <1.1) for all parameters will be used to monitor convergence. For all models, we will report posterior medians and 95% credible intervals (CrI) for the group difference and the probability that a rapid-wean will reduce the days of opioid treatment, compared to a slow-wean intervention.

Primary outcome (H1)

Linear regression model will be used for the primary outcome with treatment group as fixed effect and as hospital random effect. We will use the following priors:

trt effect ~ Normal (
$$\mu = 0, \sigma = 3$$
)
Intercept ~ Normal ($\mu = 0, \sigma = 10$)

All other covariates ~ Normal ($\mu = 0, \sigma = 2$)

Standard deviation of random effect (hospital) $\sim half - noraml (\mu = 0, \sigma = 1)$

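### SAP 6.5.1 cuts MCMC sampling from 30,000 to 1,000 draws per chain without a stated reason; if a slowly mixing sampler is used, the Bayesian limits would carry modest, avoidable simulation error

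*SAP*

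**What the plan says.** Both documents plan a Bayesian analysis of the primary outcome alongside the frequentist one, with the same priors for the arm effect.

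- **Run length.** Protocol 5.1.6: "We will use a burn-in of 3,000 iterations, with sampling from a further 30,000 iterations for each chain". SAP 6.5.1: "Each chain will involve 1,000 burn-in iterations and 1,000 additional iterations for each chain".
- **Chains.** Three in each. Protocol: "For each analysis, we will run three MCMC chains with randomly drawn starting values". SAP: "Model parameter estimates will be generated by fitting three MCMC chains with randomly drawn starting chain".
- **Software.** The SAP fits the models "by using software such as PROC MCMC (SAS) or stan (RSTAN/RSTANARM package in R"). The protocol likewise allows SAS ("For SAS, the procedure will be PROC MCMC") or R, through JAGS or Stan interfaces.
- **Safeguards.** SAP 6.5.1: "Thinning will be used as necessary to reduce autocorrelation among the samples to produce good sampling of the posterior" and "Trace plots and Gelman-Rubin convergence diagnostics (Rhat <1.1) for all parameters will be used to monitor convergence". The protocol has the same two provisions. Neither document sets a minimum effective sample size or a Monte Carlo error limit.
- **Reported quantities.** Posterior median, 95% credible interval and the probability that rapid weaning shortens treatment.

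SAP 6.5.1 does not explain the shorter run, and the revision history in SAP 1.3 does not mention it. SAP 6.5.2 (skeptical and enthusiastic priors) states no other sampler settings, so the short run presumably applies there too.

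**The concern.** SAP 6.5.1 gives the limited sample size as the reason for the Bayesian analysis, and Protocol 5.1.6 introduces these analyses in case enrollment falls short. Enrollment was ended by date, so these results are likely to be read closely. Interval limits and a probability of benefit should be properties of the data, model and prior, not of the random seed.

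A run of 3 x 1,000 draws can suffice when successive draws are nearly independent. It may not when they are strongly autocorrelated, and the SAP fixes the run length without fixing the sampler. The stated safeguards do not fill that gap. Thinning a chain of fixed length discards draws and adds no information. Rhat compares chains with one another and does not measure how precisely a tail quantile is estimated.

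**Working it through.** **Inputs.** SD 6.2 days, difference 2.0 days, target 302 infants (SAP 3.4); arm-effect prior Normal(0, SD 3) (SAP 6.5.1); run lengths as quoted. Three inputs are assumptions:
- 302 infants analyzed. This was the target before enrollment was ended by date.
- 20 hospitals. Protocol 5.3 says only that this number expressed interest.
- A random-walk sampler. The documents do not say which algorithm any package would use.

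**The plan's own figure.** n per arm = 2(z₀.₉₇₅ + z_power)² x 6.2² / 2.0². At 80% power this gives 151 per arm, 302 in total; at 90%, 202 per arm, 404 in total. Both match SAP 3.4. The iteration counts are choices and have no derivation to reproduce.

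**Loss of draws.** Protocol 3 x 30,000 = 90,000; SAP 3 x 1,000 = 3,000. The ratio is 30, so Monte Carlo error for the same sampler rises by √30 = 5.5.

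**Width of the posterior** (hospital effect ignored here, included in the simulations). SE = 6.2 x √(2/151) = 0.714 day. Posterior SD = 1/√(1/0.714² + 1/3²) = 0.694 day. Half-width of the 95% interval = 1.96 x 0.694 = 1.36 days.

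**Monte Carlo error of a 95% limit.** MCSE = √(0.025 x 0.975 / ESS) / 0.0584 x 0.694, where ESS = total draws / autocorrelation time.

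| Autocorrelation time (assumed) | SAP ESS | SAP MCSE, days | Protocol ESS | Protocol MCSE, days |
|---|---|---|---|---|
| 1 (independent) | 3,000 | 0.034 | 90,000 | 0.006 |
| 5 | 600 | 0.076 | 18,000 | 0.014 |
| 10 | 300 | 0.107 | 9,000 | 0.020 |
| 20 | 150 | 0.151 | 4,500 | 0.028 |
| 30 | 100 | 0.185 | 3,000 | 0.034 |

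**Direct simulation.** Generic random-walk Metropolis samplers were run on the H1 model (arm, random hospital intercept, SAP priors, 302 infants, 20 hospitals), rerun with new seeds on the same data.
- At the SAP length, the seed-to-seed SD of a limit was 0.08 to 0.14 day across differently tuned samplers. Effective draws for the arm effect were about 110 to 300 of 3,000.
- For one sampler, 100 reruns gave SDs of 0.138 day (lower limit) and 0.121 day (upper). The lower limit ranged from -3.98 to -3.35 and the upper from -1.29 to -0.50. At the protocol length, 30 reruns of the same sampler on the same data gave 0.027 and 0.025 day.
- These observed SDs are preferred to the table. The table applies one ESS throughout and overstates the error when it uses the ESS for the mean: at 110 effective draws it gives 0.034 x √(3,000/110) = 0.18 day, against 0.12 to 0.14 observed.

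**Probability of benefit.** MCSE = √(p(1-p)/ESS). At p = 0.95 this is 0.014 with 250 effective draws and 0.021 with 110. A simulation with a mid-range probability gave a seed-to-seed SD of 0.027. In another, 100 reruns on one dataset gave probabilities from 0.903 to 0.967. Near 1 the error vanishes: where the mean was 0.9997, the SD was 0.001.

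**Do the safeguards catch it?** In all 100 reruns of the sampler detailed above, treatment-effect Rhat was below 1.1 (maximum 1.088). Better-tuned samplers never exceeded 1.02 or 1.031. Approximately, Rhat = 1.1 with three chains corresponds to an ESS of only 3/(1.1² - 1) = 14. The SAP applies the rule to all parameters, so that was checked too. The full rule flagged 35% of runs with one sampler, and 5 of 40 and 0 of 40 with another. Among runs that passed every Rhat check with the first of these, the error was still 0.08 to 0.11 day.

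**The case against.** The strongest reply is that nothing here need go wrong. The SAP allows Stan, and with near-independent draws 3 x 1,000 gives about 0.034 day per limit, or 0.034/1.36 = 2.5% of the half-width. That stands: the error is conditional on the sampler. A reader might infer that the reported credible limits will be unreliable. The documents do not support this, because they neither commit to PROC MCMC nor say what algorithm it would use. The simulations describe generic samplers, not that procedure.

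A reader might also infer that the trial's main conclusion is exposed. It is not. SAP 6.5.1 makes the Bayesian analysis additional to the frequentist one, and the primary test comes from the linear mixed model (SAP 4.1), which MCMC length cannot affect.

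The size is also modest: 0.08 to 0.14 day is about 2 to 3 hours. If the probability of benefit is close to 1, as under a true 2-day effect, it barely moves. Nor is Rhat below 1.1 a SAP departure, since the protocol has the same threshold. Mixing of the hospital SD varied widely between samplers and it is not among the headline quantities, so no weight is placed on it.

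One defense does not hold. Thinning would help only if the run were lengthened to leave 1,000 retained draws, but the SAP specifies 1,000 iterations. If retained draws were meant, the text needs to say so.

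**Conclusion.** The point holds as a minor one. The two documents set different run lengths for the same analysis, the difference is unexplained, and simulation error is about 5.5 times larger under the SAP for any given sampler. Whether that matters depends on software the SAP leaves open: about 0.03 day per limit with near-independent draws, and about 0.08 to 0.14 day (6 to 10% of the 1.36-day half-width) with a slowly mixing random-walk sampler. In the latter case a probability of benefit away from 0 or 1 would carry about 0.01 to 0.03. This could move a limit lying near zero or change the second digit of the probability, but no more. The sizes rest on the assumed sampler, 302 infants and 20 hospitals; fewer infants would widen the posterior and scale the error up. The planned checks would not reliably reveal the error.

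**What to change.** Do one of the following in SAP 6.5.1:

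1. Restore the protocol's 3,000 burn-in and 30,000 sampled iterations for each of the three chains; or
2. Keep short runs only if a stated minimum effective sample size, or a Monte Carlo error limit, is met for the reported median, both 95% limits and the probability of benefit, extending runs until it is. As an illustration, an effective sample size of 1,000 for the limits would hold their error to 0.034 x √(3,000/1,000) = 0.06 day. The threshold is the team's choice; neither document gives one.

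Under the second option, also record the reason for departing from the protocol. Under either, say that the settings cover sensitivity analyses (1) and (2) and the alternative priors in SAP 6.5.2. The cost is minutes of computing; no data, design or primary analysis changes.

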6.5.2 Bayesian Sensitivity Analysis

The primary outcome will be analyzed using skeptical and enthusiastic priors. The skeptical prior will be centered at a mean difference of 2 and the enthusiastic prior at a mean difference of -2. In both cases $\sigma = 3$. All other priors will be set in a similar manner to the primary analysis.

Skeptical trt effect ~Normal ($\mu = 2$, $\sigma = 3$)

Enthusiastic trt effect ~ Normal ($\mu = -2, \sigma = 3$)

6.6 Missing Data

6.6.1 In-hospital data

Analysis will be completed on the ITT principle, so data will be analyzed as randomized. No imputation for missing outcome data is planned, so the analysis will be based on the Full Analysis Set.

6.6.2 Follow-Up data

For follow-up measures obtained under provision of consent, the study team will continue its commitment to data quality. When missing data are present, we will investigate the missing data pattern to see if the dropouts are independent of observed data. An exploratory approach to examine missingness mechanisms will be explored using logistic regression to identify potential participant characteristics associated with presence of missing data. In the event of large amounts of missingness for a given outcome or influential covariate, according to an agreed upon pre-specified threshold (e.g., more than 5%), we will explore multiple imputation analyses^{3,4}. We will also examine rate of missing data for all variables, site, or intervention arm. For data missing-at-random (MAR) or missing-not-at-random (MNAR), we will use selection models such as MNAR Dale or Diggle- Kenward model.22 These models often require strong assumptions about the dropout mechanism, which are unverifiable using the observed data. We will conduct sensitivity analyses to investigate the sensitivity of our conclusion to possible violation of such assumptions. For covariates for which the MAR assumption is justified, multiple imputation using sequential regression techniques will be implemented. All models will be fitted to each imputed data set and results combined using Rubin's rules that account for variability across imputations³.

6.7 Statistical Software

SAS and R

6.8 List of Potential Displays

- Figure 1: Consort Diagram
- Table 1: Maternal Demographic Characteristics of Enrolled Infants Participants
- Table 2: Demographic Characteristics of Enrolled Infant Participants
- Table 3: In-Hospital Outcomes
- Table 4: Adverse and Serious Adverse Events
- Table 5: Protocol deviation/protocol violation Summary
- Table 6: In Hospital Status
- Table 7: Bayley scores represented using cutoffs specified in section 2.2.1

• Additional tables to report model results as specified in section 6.4.1 may be provided

6.9 Reporting

Unless required by a journal, the following rules are standard:

- Moment statistics including mean and standard deviation will be reported at 1 more significant digit than the precision of the data.
- Order statistics including median, min and max will be reported to the same level of
 precision as the original observations. If any values are calculated out to have more
 significant digits, then the value should be rounded so that it is the same level of
 precision as the original data.
- Following SAS rules, the median will be reported as the average of the two middle numbers if the dataset contains even numbers.
- Test statistics including t and z test statistics will be reported to two decimal places.
- P-values will be reported to 3 decimal places if > 0.001. If it is less than 0.001 then report '<0.001'.

7 References

- 1. E9(R1) Statistical Principles for Clinical Trials: Addendum: Estimands and Sensitivity Analysis in Clinical Trials (fda.gov)
- 4. 21. Mehta A, Forbes KD, Kuppala VS. Neonatal Abstinence Syndrome Management From Prenatal Counseling to Postdischarge Follow-up Care: Results of a National Survey. Hosp Pediatr 2013, 3(4): 317-323.
